The rationale for an expedited weaning protocol is based in part on the observation that after access of the femoral artery for an angiographic procedure the standard to attain hemostasis without the use of a percutaneous closure device is manual pressure at the puncture site for 15 minutes. Since the radial artery, in contradistinction to the femoral artery, is superficial and readily compressible due to the flat surface of the radius, it is counterintuitive that to attain hemostasis pressure at the radial puncture site, pressure would need to be maintained for 60 minutes. In addition, Pancholy et al concluded based on a retrospective study of 10 consecutive patients undergoing transradial coronary angiography that “shorter duration of hemostatic compression is associated with a lower incidence of early and chronic RAO, without increase in bleeding complications.”

The standard of care (control) group in the study will consist of the subset of patients wherein the time to weaning of the TR-Band is 60 minutes.

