### **Study Endpoints**

The study participants will be randomly assigned into one of two groups; these groups will be defined based on the time from inflation to initiation of deflation of the TR-Band, i.e. the time to wean.

Group A (Total time about 60 minutes)	Group B (Total time about 120 minutes)
TR-Band Placed following your procedure	TR-Band Placed following your procedure
After 15 minutes deflated by 1/4	After 60 minutes deflated by 1/4
After 25 minutes deflated by 1/2	After 75 minutes deflated by 1/2
After 35 minutes deflated by 3/4	After 90 minutes deflated by 3/4
After 45 minutes deflated completely	After 105 minutes deflated completely
Observe your wrist for 15 minutes	Observe your wrist for 15 minutes
Remove TR-Band after 60 minutes	Remove TR-Band after 120 minutes

The primary outcomes will be the incidence of significant hematomas (> 5 cm in size), bleeding (continued ooze requiring re-inflation of the TR-Band or subcutaneous ecchymosis without a discernable hematoma) and occlusion of the left radial artery (based on ultrasound) at the procedure visit and at one month follow up visit

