## **Study Design/Methods**

Following approval of the methodology by IRB we will conduct a randomized, single center study of up to 30 subjects who undergo an angiographic procedure via the radial artery. Those patients who meet the inclusion criteria will be randomly assigned to one of two groups (A or B) based upon a standard randomized process using pre-designated sealed envelopes.

Pre-procedure, all patients participating in the study will be evaluated with a Barbeau test and a sonogram of the radial artery to determine the caliber of the vessel (in mm) and the distance (in mm) from anterior wall of the vessel to the skin surface. In addition, updated INR, PT and platelet count (within 14 days) and if applicable pre-procedure management of anticoagulants will be reviewed. All these variables will be documented in the TR-Band Form.

Intra-procedure, all patients participating in the study will receive conscious sedation with midazolam and fentanyl - dosage at the discretion of the operator. Once the area around the puncture site is infiltrated with less than 1 mL of 1% lidocaine, the radial artery will be cannulated with a 21-gauge needle using a modified Seldinger technique (i.e. a single wall puncture). The needle will subsequently be exchanged over a 0.021-inch wire for a hydrophilic-coated 5 Fr x 10 cm Glidesheath Slender sheath. Patients will then receive 200 micrograms of intra-arterial nitroglycerin and an initial bolus of 3000-5000 units of intra-venous heparin. Of note, patients undergoing a transradial uterine artery embolization will also receive 2.5 mg of intra-arterial verapamil. During the procedure patients will receive additional boluses of 1000 units of intra-venous heparin at 30-minute intervals. Prior to removal of the sheath, a second dose of 200 micrograms of intra-arterial nitroglycerin will be administered and an ACT value will be measured. After the sheath is removed, hemostasis will be attained with a TR-Band. The TR-Band consists of a part-rigid, Velcro-secured wristband with an inflatable bladder that provides compression of the radial artery when air is injected into the cuff-valve system via the supplied syringe.

Group A (Total time about 60 minutes)	Group B (Total time about 120 minutes)
TR-Band Placed following your procedure	TR-Band Placed following your procedure
After 15 minutes deflated by 1/4	After 60 minutes deflated by 1/4
After 25 minutes deflated by 1/2	After 75 minutes deflated by 1/2

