After 35 minutes deflated by 3/4	After 90 minutes deflated by 3/4
After 45 minutes deflated completely	After 105 minutes deflated completely
Observe your wrist for 15 minutes	Observe your wrist for 15 minutes
Remove TR-Band after 60 minutes	Remove TR-Band after 120 minutes

If bleeding were to occur, the TR-Band will be re-inflated to the previous volume and the weaning protocol will be restarted after 15 minutes. Once the TR-Band is removed the patient will be re-evaluated for complications including hematoma, ecchymosis and occlusion.

Post-procedure, patients will return to the clinic 1 month following their procedure and be re-evaluated for radial access complications including hematoma, ecchymosis and occlusion; and for re-evaluation of the Barbeau test, and ultrasound.

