## **Data Management**

The data from living human subjects will include the physical examination, laboratory, and ultrasound data collected both immediately before and after the procedure; these include the pre-procedure History and Physical note, the procedure report, nursing notes and clinic Progress notes.

Only IRB approved team members will have access to the records of the patient's involved, which should be effective in controlling the confidentiality of the study. Individual, unique patient codes will be utilized in an Excel data spreadsheet for anonymization and subsequent analysis. These patient codes will be stored in a separate, secure location at the VIR Research Coordinator Office. The patient's safety will be ensured by the following methods. Prior to discharge from the PACU the patients will be given the contact information of the VIR Nurse Coordinator and clinic for any concerns. In addition, in the case of emergency, a VIR team of physicians and staff are on call at all times (24/7) to manage any acute or emergent patient issues.

The patients' characteristics (e.g. demographic information) will be compared using a t-test or chi-squared tests. The primary outcomes, i.e. rates of complications will be compared using a McNemar's test. An odds ratio will be estimated and its 95% confidence interval reported. Associations between preoperative factors and complications will be evaluated using logistic regression with random effects to account for multiple observations per patient.

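### The only test named for the primary complication rates is McNemar's, a paired test, but the trial has two separate randomised groups and defines no pairs

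*Combined protocol and SAP*

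**What the plan says.** The analysis plan is the last paragraph of the Data Management section. For the primary outcomes it states that "rates of complications will be compared using a McNemar's test". It adds an odds ratio with a 95% confidence interval, without saying whether this is paired or unpaired. No other test is named for the primary outcomes.

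The design is described in three places:

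- Study Endpoints: "The study participants will be randomly assigned into one of two groups", the groups being defined by time to wean.
- Study Design/Methods: eligible patients "will be randomly assigned to one of two groups (A or B) based upon a standard randomized process using pre-designated sealed envelopes".
- Intervention to be Studied: "The standard of care (control) group in the study will consist of the subset of patients" weaned at 60 minutes.

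The one repeated measurement described is over time. Study Endpoints has the outcomes assessed "at the procedure visit and at one month follow up visit", and Study Design/Methods says "patients will return to the clinic 1 month following their procedure and be re-evaluated for radial access complications".

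**The concern.** McNemar's test compares two binary measurements within a pair and uses only the discordant pairs. A trial with two independent groups has no such pairs, so the analyst would have to make them up or apply the test to something else. The protocol does not say which. Two of the three possible applications do not compare A with B at all. The third makes the p-value depend on a choice that nobody has specified.

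This is the primary analysis of the safety question. The planned odds ratio could still be a valid unpaired estimate, but the McNemar p-value reported beside it would not correspond to it. With at most 30 patients a handful of events decides the result, so the choice of test matters. Switching to another test once the data are in would be an unplanned change to the primary analysis.

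**Working it through.** The documents give no power calculation, event rate for planning or significance level, so there is no stated figure to reproduce. The check sets the test against the design and then shows what each possible application would do.

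**Inputs.** Number of Subjects gives up to 30 patients in total. Assumptions: 15 per arm, two-sided 0.05, exact tests, and a range of event risks.

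**Formula.** With discordant counts b and c, exact McNemar p = min(1, 2 × P(Bin(b + c, 0.5) ≤ min(b, c))).

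**(i) Pair each patient's procedure visit with the one-month visit.** Here b counts events that resolve and c counts events that appear later. Group does not enter.

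- A 8/15, B 0/15, all events persisting: b = c = 0, so p = 1.0. Fisher for A v B gives 0.0022.
- A 4/15, B 4/15, all events resolved by one month: b = 8, c = 0, so p = 2 × 0.5⁸ = 0.0078. Fisher for A v B gives 1.0.

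A large difference between arms is missed in the first case. In the second, a significant result appears with no difference at all.

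**(ii) Enter the arm-by-outcome 2×2 table as if it were paired.** With x events in A and y in B, the off-diagonal cells are 15 − x (no event in A) and y (event in B). These have no reason to be equal when the risks are equal. For 2/15 v 2/15 the cells are 13 and 2, giving p = 0.0074 (Fisher 1.0). The table below enumerates all outcomes with the same true risk in both arms.

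**(iii) Pair A patients with B patients blind to outcome.** Under equal risk p, each type of discordant pair has probability p(1 − p), and there are 15 pairs.

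Probability of p ≤ 0.05 when both arms have the same true risk:

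| True risk in both arms | (ii) arm-by-outcome table | (iii) outcome-blind pairs | Fisher |
|---|---|---|---|
| 6% | 99.8% | 0.01% | 0.1% |
| 10% | 97.4% | 0.1% | 0.6% |
| 20% | 62.4% | 0.8% | 1.7% |
| 30% | 17.9% | 1.4% | 1.7% |
| 40% | 2.2% | 1.8% | 1.6% |
| 50% | 0.2% | 1.8% | 1.7% |

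Application (iii) is valid, but its answer is not fixed by the data. Take 7/15 v 1/15:

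- If the one B event is paired with an A event (chance 7/15 under random pairing): b = 6, c = 0, p = 2 × 0.5⁶ = 0.031, and the paired odds ratio is infinite.
- Otherwise: b = 7, c = 1, p = 2 × (1 + 8) × 0.5⁸ = 0.070, and the paired odds ratio is 7/1 = 7.
- Unpaired, there is one answer: Fisher p = 0.035, odds ratio (7 × 14)/(8 × 1) = 12.25.

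**The case against.** The strongest counter-argument comes from the same paragraph of the plan. The risk-factor regression there has random effects because a patient may contribute more than one observation, so the authors expected correlated data. That no patient is randomised twice is also an inference from assignment to one of two groups; the protocol does not say so in words. Both observations are correct, but neither supplies an A-B pair. If the repeated observations are the two visits, both fall in the same arm. If they are repeat procedures, nothing says that a patient would receive both schedules.

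Some points on size also stand:

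- Application (ii) is a misuse that no text in the protocol suggests. It shows what could go wrong and is not a prediction.
- The event counts in (i) are high for complications that the Background calls rare. The Background does cite a 6% occlusion rate from an early coronary series, though not as a planning value.
- Application (iii), the one that compares arms, does not inflate false positives.
- The trial can settle little with any test. For assumed risks of 30% v 10% at 15 per arm, power is 15% with Fisher and 9% with outcome-blind McNemar pairs.

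These points limit the practical damage. They do not make McNemar's test a comparison of Group A with Group B.

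**Conclusion.** The concern holds. The sole test named for the primary outcomes does not fit the randomised design, and the protocol contains nothing that would make it fit. The error is in the rule as written; it is more than a missing detail.

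The mismatch itself rests on the text alone. The illustrations of its size rest on the assumed 15 per arm, 0.05 level and event counts. Depending on how the test is applied, it ignores the arms, rejects equality in 0.2% to 99.8% of trials with equal risks, or gives a valid p-value that varies with an arbitrary pairing. The correction must be made before the primary outcomes are analysed.

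**What to change.** In the Data Management section, replace the McNemar sentence with wording such as:

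> The proportion of patients with each primary outcome will be compared between Groups A and B, as randomised, at the procedure visit and at one month, using a two-sided Fisher's exact test.

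Boschloo's unconditional exact test would serve equally well if it is the one named in advance. Take the planned odds ratio and its 95% confidence interval from the same unpaired table; a risk difference may be added. Because the unit is the patient, the comparison does not treat repeated observations as independent. The outcomes and visits are those already listed under Study Endpoints, so the change adds no endpoint. The risk-factor model can stay as it is. If a paired design was in fact intended, the protocol would have to describe the pairs, which it does not do now.

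The cost is the rewording of one sentence, with no new data and no extra patients. Fisher's test is conservative at this size (1.7% or less in the table above), but it gives a single answer to the question the trial asks.

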## **Objectives/Specific Aims**

The specific aim of the study is to evaluate the safety and efficacy of initiating earlier TR-Band weaning following transradial access procedures, while minimizing access site complications including hematoma formation and radial artery occlusion (RAO).

The primary objective is to evaluate the rate and severity of complications (i.e. hematoma, ecchymosis and radial artery occlusion) from an expedited weaning protocol wherein the time to wean is reduced significantly.

The secondary objective is to identify potential risks factors for complications following early weaning of the TR-Band.

It is hypothesized that the time to wean of the TR-Band can be safely reduced while minimizing access site complications including hematoma formation and radial artery occlusion (RAO).

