## **Background**

The use of transradial (TR) access for the purpose of diagnosis and intervention in the arterial system is a well-established concept, particularly in coronary angiography, with many distinct advantages over conventional transfemoral (TF) access. The first series of 100 coronary angiographic procedures performed via TR access, published by Campeau in 1989, demonstrated 88% technical success rate and a 6% asymptomatic radial artery occlusion rate. Since then, TR access for coronary artery interventions in the United States has grown exponentially with the proportion of transradial percutaneous coronary interventions (PCI) procedures increasing from 1.2% in the first quarter of 2007 to 16.1% in the third quarter of 2012. And yet, its usage is largely absent in the interventional radiology and vascular surgery communities. Reasons for this include a lack of appropriate training and equipment, but the potential advantages of TR over TF access are abundant in both coronary and non-coronary applications. Firstly, the radial artery is more superficial than the femoral artery without surrounding neurovascular structures susceptible to injury. In addition, any sustained arterial damage is significantly less detrimental because of the hand's dual arterial vascular supply. In addition, the radial artery is readily compressible regardless of the patient's body habitus. This compressibility has been shown to decrease the incidence of post-procedural bleeding complications as well as cardiac mortality during PCI. In addition to patient safety, there are numerous benefits to overall patient comfort and convenience. For one, after TR access, patients may sit up in bed and ambulate immediately with faster discharge to home. In one randomized trial, Cooper et al demonstrated a strong patient preference, improved quality-of-life metrics, and decreased hospital costs for TR over TF access during cardiac catheterization.

Ultimately, complications with TR approach have proven rare in both coronary and noncoronary applications. Most commonly, a local small hematoma may develop with

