## **Number of Subjects**

The study cohort will consist of up to 30 enrolled and randomized patients age 18 years and older who undergo an angiographic procedure via the radial artery. The proposed study does not include children.

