#### **Potential Benefits to Subjects or Others**

The potential benefits to the patients include a shorter PACU recovery times, less postoperative discomfort related to the insufflated TR-Band, and lower cost. The preoperative physical, laboratory and ultrasound examination will also help to clarify patient criteria for indications and contraindications for Expedited TR Band deflation by identifying demographic and anatomic risk factors for complications.

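### For rare or persisting complications such as occlusion, random-effects logistic regression on at most 30 patients is unstable and can report very large odds ratios for factors with no effect

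*Combined protocol and SAP*

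**What the plan says.** The secondary objective (Objectives/Specific Aims) is: "The secondary objective is to identify potential risks factors for complications following early weaning of the TR-Band". One sentence in Data Management provides its analysis: "Associations between preoperative factors and complications will be evaluated using logistic regression with random effects to account for multiple observations per patient".

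Other sections determine what data that model would receive:

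- Number of Subjects: "The study cohort will consist of up to 30 enrolled and randomized patients".
- Study Endpoints: outcomes are assessed "at the procedure visit and at one month follow up visit". No other repeated observation of the outcomes is described.
- Study Design/Methods: seven variables are recorded before the procedure, namely Barbeau result, artery caliber, artery depth, INR, PT, platelet count and anticoagulant management. Of these it says: "All these variables will be documented in the TR-Band Form".
- Background: complications are called rare. The one numeric rate comes from a historical coronary series of 100 procedures, which "demonstrated 88% technical success rate and a 6% asymptomatic radial artery occlusion rate".
- Potential Benefits to Subjects or Others: the preoperative examinations will "help to clarify patient criteria for indications and contraindications for Expedited TR Band deflation".

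The plan does not give an expected number of events, say whether factors enter singly or jointly, limit their number, or say what happens if the model does not converge.

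**The concern.** A random intercept separates variation between patients from variation within a patient. Here every candidate factor is fixed within the patient, so the second record adds almost nothing about it. If the outcome also persists, as an occlusion may, the two records are near copies. The likelihood can then explain the data by an ever larger between-patient variance, and the coefficients grow with it. Few events make this worse.

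This is the only analysis that serves the secondary objective. The Potential Benefits section also expects the study to clarify who is suited to expedited deflation. A table with an odds ratio of 30 or more for an irrelevant factor would be easy to over-read. With no fallback stated, the model would end up being chosen after the data are seen.

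**Working it through.** The plan has no event count, power or sample-size calculation to reproduce. Event rates, persistence and factor distributions below are assumptions, shown as ranges.

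**1. Expected events.** With n = 30 and rate p, the expected number is 30p, and P(0 or 1) = (1−p)^30 + 30p(1−p)^29.

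- p = 6% (the Background figure): 1.8 expected; 0.1563 + 0.2992 = 0.455.
- p = 10% (assumed): 3.0 expected; 0.0424 + 0.1413 = 0.184.

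**2. A ceiling at any rate.** With 30 patients the smaller outcome class cannot exceed 15. Seven factors then have at most 15/7 = 2.1 patients each. If the objective is read literally as the early-weaning group only (about 15 patients if allocation is 1:1, which is not stated), this falls to about 1.

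**3. Random-intercept model, two visits, one continuous factor with no effect.** Simulations used 80 to 150 trials per setting where recorded. Odds ratios are per SD of the factor and folded above 1. Where two values appear, they come from separate runs.

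| Rate, share persisting to one month | Random-effect SD above 5 | Median odds ratio |
|---|---|---|
| 6%, 80% | 71% to 85% | 38 to 45 |
| 10%, 80% | about 86% | 32 to 36 |
| 20%, 80% | 84% | not recorded |
| 6%, 40% | 29% | 2.5 |
| 10%, 40% | 34% | 2.3 |
| 20%, 10% | 0% | 1.3 to 1.5 |

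A further set of fits at 80% persistence gave 83% to 98% over rates of 6% to 20%, so the overall range is roughly 70% to 98%. At 80% persistence the null odds ratio was above 10 or below 0.1 in about 48% to 71% of trials. A 20% rate does not rescue the model if the outcome persists. The exact medians at high persistence depend on optimiser limits; the pattern does not.

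A milder set-up assumed a true random-intercept SD of 1.5 (200 runs per setting). Problem-free means that neither the variance nor the odds ratio was degenerate.

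| Rate at procedure, then one month | Null odds ratio above 10 or below 0.1 | Problem-free |
|---|---|---|
| 10%, 6% | 23% | 28% |
| 20%, 10% | 14% | 60% |
| 40%, 20% | 10% | 75% |

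In the first row the SD collapsed to about zero in 42% of runs and rose above 8 in 23%. Collapse simply returns ordinary logistic regression. It is not a failure to fit, but it shows how little the data say about the variance.

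**4. How much is scale.** A random-intercept odds ratio is conditional on the patient. Dividing its logarithm by √(1 + 0.346·SD²) puts it roughly on the marginal scale. At SD = 5 the divisor is √(1 + 0.346 × 25) = √9.65 = 3.1. In the runs with medians of 45 (6%) and 32 (10%), rescaling gave 1.6 and 1.5. A Firth fit with one record per patient gave about 1.3 to 1.7.

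**5. False positives.** Likelihood-ratio tests of the null factor rejected in about 5% to 13% of trials, against a nominal 5%.

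**6. If the seven factors were entered together.** With one record per patient and no true effects, two simulations with different factor distributions found no finite maximum-likelihood estimate (no events, or separation) in 92% and 97% of trials at 6%, 82% and 90% at 10%, and 49% and 59% at 20%.

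**7. One factor at a time, ordinary maximum likelihood.** A continuous factor had no finite fit in 17%, 5% and about 0% of trials at 6%, 10% and 20%. A binary factor with 15% prevalence was separated in 65%, 62% and 43%. Dropping the random effect is therefore not enough by itself; a penalised or exact method is also needed.

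**The case against.** The plan has a fair defence. Two assessments per patient are planned, so a random effect has a basis. No trial event rate or persistence rate is given. The 6% concerns occlusion in a historical coronary series, and the bleeding outcome includes ooze and ecchymosis, which may be more frequent. Ooze that requires re-inflation can occur only while the band is on, so it cannot be duplicated at one month. For such an outcome the model behaved well in step 3. All of this stands, and it limits the point to rare or persisting outcomes.

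A reader might infer more than the documents support in three ways:

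- **That the model must either fail or return huge odds ratios.** This is too absolute. It depends on rate and persistence, and many of the settings above give ordinary, if imprecise, fits.
- **That a joint seven-factor model is planned.** Data Management does not say so. Fitting factors one at a time is an equally fair reading, so step 6 is conditional.
- **That false risk factors would routinely be declared, or that the regression will decide who is weaned early.** Step 5 shows only modest inflation of the test. No section uses the regression to select patients, the objective speaks only of potential risk factors, and the Potential Benefits section does not mention the regression.

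The contrast between odds ratios of about 37 and 1.5 is also largely conditional against marginal scale. It is not evidence that Firth estimation removes that much error. What remains is that the analyst would print the conditional odds ratio, and few readers would rescale it.

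**Conclusion.** The concern holds in a limited form. For rare or persisting complications such as occlusion, the stated model is poorly identified with at most 30 patients and two assessments each. Assuming 80% persistence and rates of 6% to 20%, the random-effect SD runs above 5 in roughly 70% to 98% of trials, and the reported odds ratios for null factors would mislead. For transient or more common outcomes the model usually fits but is imprecise. If all seven factors were entered together, about 80% to 97% of trials at rates of 6% to 10% would have no finite estimate, but the plan leaves that choice open.

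This is a should-fix. It affects the secondary objective and leaves the primary comparison untouched. Its size rests on the assumed rates and persistence. The binomial figures, the ceiling of 15, and the absence of any stated fallback do not depend on persistence.

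**What to change.** Replace the risk-factor sentence in Data Management with wording such as:

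> For each complication, each patient contributes one record (any event through one month: yes or no). Associations with preoperative factors are estimated one factor at a time by Firth-penalised logistic regression with profile-likelihood 95% intervals, or by exact logistic regression for binary factors. No random effect is used. If an outcome has fewer events than a stated minimum, factors are described only. Events are tabulated separately for the procedure visit and one month. These analyses are exploratory.

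The sponsor should choose the minimum and state it before data are seen; no particular cut-off follows from the documents. The separate tabulation keeps the timing set out in Study Endpoints. The same exploratory label should appear in Objectives/Specific Aims and in Potential Benefits.

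The cost is a few sentences and routine software, with no new data. The downside is that there is no mutually adjusted model and the claim is more modest.
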